#### 4.3. Exclusion Criteria

Subjects will be excluded from the study if any of the following exclusion criteria apply prior to randomization:

- 1. Any uncontrolled or serious disease, or any medical or surgical condition, that may either interfere with participation in the clinical study, and/or put the subject at significant risk (according to investigator's [or delegate] judgment) if he/she participates in the clinical study.
- 2. An underlying known disease, or surgical, physical, or medical condition that, in the opinion of the investigator (or delegate) might interfere with interpretation of the clinical study results.
- 3. New York Heart Association (NYHA) class IV heart failure or last known left ventricular ejection fraction <25%.
- 4. Cardiac arrhythmia within 3 months prior to randomization that is not controlled by medication or via ablation.
- 5. Major adverse cardiovascular event within 3 months prior to randomization.
- 6. Uncontrolled severe hypertension: systolic blood pressure >180 mmHg or diastolic blood pressure >110 mmHg prior to randomization despite anti-hypertensive therapy.
- 7. Active liver disease defined as any known current infectious, neoplastic, or metabolic pathology of the liver or unexplained elevations in ALT, aspartate aminotransferase (AST), >3x the ULN, or total bilirubin >2x ULN at screening confirmed by a repeat abnormal measurement at least 1 week apart.
- 8. Severe concomitant noncardiovascular disease that carries the risk of reducing life expectancy to less than 2 years.
- 9. History of malignancy that required surgery (excluding local and wide-local excision), radiation therapy and/or systemic therapy during the three years prior to randomization.
- 10. Females who are pregnant or nursing, or who are of childbearing potential and unwilling to use at least two methods of highly effective contraception (failure rate less than 1% per year) (eg combined oral contraceptives, barrier methods, approved contraceptive implant, long- term injectable contraception, or intrauterine device) for the entire duration of the study. Exemptions from this criterion:
  - a. Women >2 years postmenopausal (defined as 1 year or longer since last menstrual period) AND more than 55 years of age.
  - b. Postmenopausal women (as defined above) and less than 55 years of age with a negative pregnancy test within 24 hours of randomization.
  - c. Women who are surgically sterilized at least 3 months prior to enrollment.

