# 4.5. Stopping Criteria

#### 4.5.1. Individual Subject Dosing Stopping Criteria

During the double-blind, active treatment phase subjects will have clinic visits at regular intervals. Dosing with blinded study medication (inclisiran and/or matching placebo) should be temporarily discontinued or stopped in subjects with:

- 1. Intolerable adverse events, or if the Investigator believes that continuing dosing will be detrimental to the subject's mental or physical health. This includes severe or serious reactions at the injection site and any anaphylactic type reactions.
- 2. Unexplained increases in transaminases (ALT or AST) or total bilirubin as follows:
  - a. ALT or AST >8xULN
  - b. ALT or AST >5xULN for more than 2 weeks
  - c. ALT or AST >3xULN and (total bilirubin >2xULN or INR >1.5)
  - d. ALT or AST >3xULN with the appearance of fatigue, nausea, vomiting, right upper quadrant pain or tenderness, fever, rash, and/or eosinophilia (>5%)

The investigator should evaluate to see if other causes for the laboratory abnormalities are immediately apparent, such as obstructive gall bladder or bile duct disease, viral or alcoholic hepatitis, malignancy involving the liver, congestive hepatopathy, other hepatotoxins or heritable disorders.

3. Unexplained creatine kinase (CK) values >5 x ULN confirmed by repeat test when the CK elevation is associated with muscle pain, muscle tenderness and/or muscle weakness, or new onset renal dysfunction.

In the case that study medication is permanently discontinued the subject will be asked to complete the remainder of the scheduled visits without receiving blinded study medication (inclisiran or placebo).

All trial subjects should be followed until all abnormalities return to normal or to the baseline state.

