3.8.8.3. Chemistry

Blood draws for chemistry will be performed per the Schedule of Assessments (Table 1).

Analysis will vary based on visit day as follows:

- **Full serum chemistry - Baseline (Day 1) and EOS (Day 540)**
Aspartate aminotransferase (AST), alanine aminotransferase (ALT), alkaline phosphatase (ALP), gamma glutamyl transferase (GGT), total bilirubin (TBIL), direct and indirect bilirubin, creatine phosphokinase (CPK), lactate, bicarbonate, uric acid, creatinine, blood urea nitrogen (BUN), estimated glomerular filtration rate (eGFR), sodium, potassium, calcium, inorganic phosphate, chloride, albumin, total protein, glucose (fasting), glycated hemoglobin A1C (HbA1c), and tryptase (as required).

- **Limited serum chemistry - Screening, Days 90, 150, 270, 330, 450 and 510**
ONLY: AST, ALT, ALP, GGT, TBIL, CPK, creatinine, eGFR, fasting glucose, HbA1c (not at Day 150, 330, and 510) and tryptase (as required).

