6.3.3. Analysis Windows and Baseline

The analysis windows around each visit day are provided in [Table 2](#) below.

Table 2: Analysis Windows for Each Scheduled Visit

Scheduled Visit	Analysis Window	
	From	To
Baseline		Before randomization/First Study Treatment
Day 30	Day 1	Day 60
Day 90	Day 61	Day 120
Day 150	Day 121	Day 210
Day 270	Day 211	Day 300
Day 330	Day 301	Day 390
Day 450	Day 391	Day 480
Day 510	Day 481	Day 525
Day 540	Day 526	No upper limit

Data collected at scheduled or unscheduled visits will be used in the analysis if they fall into an analysis window for a scheduled visit. If more than one visit (scheduled or unscheduled) is made

within the window specified above for any scheduled visit, the non-missing assessment closest to the scheduled visit day will be used in the analysis for that visit. However, all data will be included in the subject data listings.

Unless otherwise specified, data collected from assessments that occur more than once prior to initiation of investigational product administration, the latest assessment will be considered the "Baseline" evaluation for analysis.

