- Non HbA1c: >1 and ≤ 3 x ULN at baseline or post baseline, resolved to $<$ ULN at any post baseline visit, and remaining $<$ ULN at final visit
- HbA1c: $\geq 6.5\%$ at baseline or $\geq 6.5\%$ and $\geq 0.5\%$ change from baseline for post-baseline, resolved to $<6.5\%$ and $<0.5\%$ change from baseline at any post baseline visit, and remaining $<6.5\%$ and $<0.5\%$ change from baseline at final visit

Separate listings of all subjects with PCS and CS laboratory values will be presented. Subjects will appear once per lab parameter but may appear under multiple lab parameters. The worst post-baseline value will be utilized in the analyses.

The number and percentage of subjects satisfying Hy's Law will also be tabulated by treatment group based on the following lab findings:

- Any elevated post-baseline aminotransferases defined as:
 - ALT > 3 x ULN or
 - AST > 3 x ULN
- Elevated post-baseline serum total bilirubin (TBL) > 2 x ULN and serum alkaline phosphatase (ALP) levels < 2 x ULN

Subjects must meet all of the criteria listed above at the same time point and have normal lab parameters (ALT, AST, TBL) at baseline to be considered a Hy's Law case.

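### The Hy's Law count leaves out eligible subjects with a raised baseline ALT, AST or bilirubin, and no other planned output combines the liver tests for them

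*SAP*

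**What the plan says.** SAP section 6.4.8.2 tabulates Hy's Law by arm. A subject needs a post-baseline ALT or AST above 3x ULN together with "serum total bilirubin (TBL) > 2 x ULN and serum alkaline phosphatase (ALP) levels < 2 x ULN". It then adds: "Subjects must meet all of the criteria listed above at the same time point and have normal lab parameters (ALT, AST, TBL) at baseline". The SAP describes no second count without the baseline condition and none that allows a time lag.

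Protocol section 4.3, exclusion 7, removes subjects with known current liver pathology. On laboratory values it removes only unexplained "elevations in ALT, aspartate aminotransferase (AST), >3x the ULN, or total bilirubin >2x ULN at screening confirmed by a repeat abnormal measurement", with the repeat at least one week apart.

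SAP section 6.3.3 defines baseline: for "data collected from assessments that occur more than once prior to initiation of investigational product administration, the latest assessment will be considered" the baseline evaluation. Where a visit window holds several values, "the non-missing assessment closest to the scheduled visit day will be used in the analysis for that visit".

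SAP section 3.8.8.3 sets the sampling: "Limited serum chemistry - Screening, Days 90, 150, 270, 330, 450 and 510", with the full panel at Day 1 and Day 540. Neither panel is drawn at Day 30.

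SAP section 6.3.1 bases percentages on subjects in the analysis set with non-missing data, unless specified otherwise.

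**The concern.** The entry rule and the case definition use different limits. A subject may enter with mildly raised transaminases or bilirubin, but the case definition requires all three tests to be normal at baseline. Such a subject is a non-case by rule, whatever happens after dosing.

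The SAP expects these subjects. Its classification of potentially clinically significant chemistry values has one category for values abnormal at baseline and another for values of 1 to 3x ULN that later exceed 3x ULN.

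The single-time-point condition narrows the count further. If bilirubin passes 2x ULN only on a sample after the one with the transaminase rise, the subject is not counted.

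The product acts in hepatocytes, and Protocol section 8.6.2 names drug-induced liver injury as a possible reason to terminate the study. A Hy's Law row showing zero would probably be read as covering all treated subjects. It would cover only those with a normal baseline.

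**Working it through.** The documents state no figure for this point, so there is none to reproduce. The check is a comparison of rules, followed by an illustration of size.

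**1. An eligible subject who cannot be counted.** Take baseline ALT 2x ULN and bilirubin 1.5x ULN. One later sample shows ALT 4x ULN, bilirubin 2.5x ULN and ALP below 2x ULN.

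| Rule | Result |
|---|---|
| Exclusion 7, laboratory limits | 2 is not above 3 and 1.5 is not above 2: not excluded |
| ALT or AST >3x ULN | 4 > 3: met |
| Bilirubin >2x ULN and ALP <2x ULN, same sample | 2.5 > 2: met |
| Normal ALT, AST and bilirubin at baseline | Not met |
| SAP Hy's Law table | Non-case |

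The exclusion is looser than its limits suggest, because an elevation must be unexplained and repeat-confirmed to exclude. Eligibility also uses screening values, whereas baseline is the latest pre-dose value, normally Day 1.

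**2. What the other outputs show for this subject.**
- The clinically significant tables count the ALT and the bilirubin value separately.
- The listings give one entry per parameter and the analyses use the worst value, so they need not show that the two rises coincided.
- The shift tables compare low, normal and high categories, so both tests fall in the high-to-high cell.
- The hepatic search in SAP Appendix 5 looks for reported adverse event terms, not combinations of laboratory values.

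**3. Timing.** Chemistry days are 1, 90, 150, 270, 330, 450, 510 and 540. Successive gaps are 89, 60, 120, 60, 120, 60 and 30 days. Of the six gaps between post-baseline samples, a 30-day window spans one at nominal days (Day 510 to 540), a 60-day window spans four and a 120-day window spans all six. Anything further depends on unscheduled samples or shifted visits.

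The SAP does not say whether *same time point* means the same sample or the same analysis window. The closest-to-scheduled-day rule could drop an unscheduled peak, while section 6.4.8.2 says the worst post-baseline value is used.

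**4. Size, by assumption.** Let p be the share with any of the three tests abnormal at baseline (not in the documents; assumed 1% to 30%). Let RR be the assumed relative risk of a true case in those subjects. The planned 750 per arm are all taken as treated.
- Not countable per arm = 750 x p
- Share of true cases not counted = p x RR / (p x RR + 1 - p)
- One-sided 95% upper bound with zero cases among n subjects = 1 - 0.05^(1/n)

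| p | Not countable per arm | In the trial | Cases not counted, RR = 1 | RR = 2 | Upper bound, countable subjects only |
|---|---|---|---|---|---|
| 1% | 7.5 | 15 | 1% | 2.0% | 0.403% |
| 5% | 37.5 | 75 | 5% | 9.5% | 0.420% |
| 10% | 75 | 150 | 10% | 18.2% | 0.443% |
| 20% | 150 | 300 | 20% | 33.3% | 0.498% |
| 30% | 225 | 450 | 30% | 46.2% | 0.569% |

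For p = 10% and RR = 2: 0.20 / (0.20 + 0.90) = 18.2%. For the bound at p = 10%: 1 - 0.05^(1/675) = 0.443%, against 1 - 0.05^(1/750) = 0.399% if all 750 are taken as covered.

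**The case against.** A normal-baseline condition is a legitimate prespecified way to isolate new liver injury. A subject with long-standing raised bilirubin needs only a small further rise to pass 2x ULN, and counting such subjects lowers specificity. The individual elevations are not hidden either. Clinically significant status requires only that baseline or earlier values had not met the same threshold, so the subject in the example appears in the tables under both tests. The data monitoring committee reviews safety every 3 months and the sponsor reviews data on an ongoing basis.

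Most of this stands. It supports keeping the normal-baseline row but not making it the only one, because a reader must cross-match per-parameter listings to find a combined abnormality.

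Three stronger readings are tempting, and the documents do not support them.
- *The trial would lose liver cases.* It would not: the data are kept and listed, and only the combined count is missing.
- *The SAP contradicts the dosing-stop rule.* Protocol section 4.5.1 has a combined ALT/AST and bilirubin trigger with no baseline condition, so a subject could meet it and be tabulated as a non-case. But that rule concerns unexplained increases, accepts INR above 1.5 in place of bilirubin and has no ALP condition. It protects the individual subject, and a rule with another purpose may differ. This point asks for no change to it.
- *One uncounted case would change the safety conclusion.* Neither document rests the conclusion on this row or gives an expected number of true cases.

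**Conclusion.** The gap holds on the text alone: a defined group of eligible, treated subjects cannot appear in the only planned count that combines the liver tests. Its size cannot be fixed from the documents. The range of 15 to 450 subjects rests wholly on the assumed share of 1% to 30%, and the shares of uncounted cases rest also on the assumed relative risk. With zero counted cases the upper bound moves only modestly, from 0.399% to between 0.403% and 0.569%. The main problem is therefore coverage: the count says nothing about the subjects it leaves out.

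The condition applies to both arms alike, so a reader should not infer a bias towards either. The concern is under-counting of a rare event. It does not touch the efficacy analyses, but the plan should be changed because the remedy is small.

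**What to change.** Amend SAP section 6.4.8.2 to tabulate, by arm:
1. Subjects with post-baseline ALT or AST >3x ULN, bilirubin >2x ULN and ALP <2x ULN at the same time point, regardless of baseline, using scheduled and unscheduled samples.
2. The current definition (normal baseline, same time point) as a subset of row 1.
3. A supplementary row in which the bilirubin rise may follow the ALT/AST rise within a prespecified window. Choose its length with the 30 to 120 day sampling gaps in mind, and state which sample the ALP condition applies to.

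Define *same time point*, and say that the closest-to-scheduled-day selection does not remove values from this table. State the denominator of each row. List every candidate with baseline values, ALP and sample dates.

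SAP section 6.4.8.3.1 already takes this approach for diabetes events, analysing all subjects and then by baseline status. No new data are needed and no existing output is lost. The downside is a few extra candidates, for example with long-standing raised bilirubin, who will need a narrative.

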6.4.8.3. Diabetes Assessment

Diabetes will be assessed by the analysis of:

- TEAEs
- change in glucose-related laboratory values over time
- shifts from baseline in glucose control category and,
- incidence of post-baseline new onset of diabetes.

Note that diabetes related tables dealing with the fasting glucose parameter will require the lab sample to be taken while fasting. Samples taken while the subject was not fasting will not be analyzed.

6.4.8.3.1. Diabetes TEAE

New onset/worsening of diabetes will be identified using SMQ and AE terms (refer to [Appendix 5](#) on Standardized MedDRA Queries (SMQ) and AE terms). The analysis will be performed for all subjects and then by baseline diabetes status. A subject will be identified as being diabetic at baseline if the targeted medical history notes that the subject is diabetic or the baseline HbA1c value is $\geq 6.5\%$.

6.4.8.3.2. Change in Glucose-related Laboratory Values Over Time

This analysis only utilizes laboratory data (fasting glucose and HbA1c). The change from baseline to the last on-treatment observation and the worst on-treatment observation will be summarized separately for fasting glucose and HbA1c overall and then by baseline glucose

control status. Baseline glucose control status will be identified separately for fasting glucose and HbA1c using the values provided in the table below (note that medical history will not be taken into account for this analysis). Figures will also be created showing mean fasting glucose and HbA1c values over time by baseline glucose control status.

Parameter	Baseline Glucose Control Status	Baseline Laboratory Values*
Fasting Glucose	Normal	<100 mg/dL
	Impaired	≥100 to <126 mg/dL
	Diabetes	≥126 mg/dL
HbA1c	Normal	<5.7%
	Impaired	≥5.7 to <6.5%
	Diabetes	≥6.5%

*Using average of Screening and Day 1 fasting glucose values. If one fasting glucose value is missing (Screening or Day 1), the assessment will be based on the available data.

6.4.8.3.3. Shifts from Baseline in Glucose Control Category

Shifts from baseline in glucose control category will be summarized two different ways. The change from baseline to the worst-on-treatment and then again for the last-on-treatment laboratory values will be used to classify the on-treatment glucose control category. Note that medical history will not be taken into account for this analysis. If consecutive fasting glucose measurements fall in two separate categories, or if only one pre- or post-baseline fasting glucose measurement is available, then the classification will be based on the HbA1c measurements only. If HbA1c is missing then both consecutive fasting glucose measurements must fall in a category otherwise the lower category will be used.

Shift Category*	Baseline Values**	Post-baseline Values
Normal to Normal (no change)	Fasting glucose <100 mg/dL on Screening or Day 1 AND HbA1c <5.7%	Fasting glucose <100 mg/dL on two consecutive occasions AND HbA1c <5.7%
Normal to Impaired	Fasting glucose <100 mg/dL on Screening or Day 1 AND HbA1c <5.7%	Fasting glucose ≥100 and <126 mg/dL on two consecutive occasions OR HbA1c ≥5.7 and <6.5%
Normal to Diabetes	Fasting glucose <100 mg/dL on Screening or Day 1 AND HbA1c <5.7%	Fasting glucose ≥126 mg/dL on two consecutive occasions OR HbA1c ≥6.5%

Impaired to Normal	Fasting glucose ≥ 100 and < 126 mg/dL on Screening and Day 1 OR HbA1c ≥ 5.7 and $< 6.5\%$	Fasting glucose < 100 mg/dL on two consecutive occasions AND HbA1c $< 5.7\%$
Impaired to Impaired (no change)	Fasting glucose ≥ 100 and < 126 mg/dL on Screening and Day 1 OR HbA1c ≥ 5.7 and $< 6.5\%$	Fasting glucose ≥ 100 and < 126 mg/dL on two consecutive occasions OR HbA1c ≥ 5.7 and $< 6.5\%$
Impaired to Diabetes	Fasting glucose ≥ 100 and < 126 mg/dL on Screening and Day 1 OR HbA1c ≥ 5.7 and $< 6.5\%$	Fasting glucose ≥ 126 mg/dL on two consecutive occasions OR HbA1c $\geq 6.5\%$
Diabetes to Normal	Fasting glucose ≥ 126 mg/dL on Screening and Day 1 OR HbA1c $\geq 6.5\%$	Fasting glucose < 100 mg/dL on two consecutive occasions AND HbA1c $< 5.7\%$
Diabetes to Impaired	Fasting glucose ≥ 126 mg/dL on Screening and Day 1 OR HbA1c $\geq 6.5\%$	Fasting glucose ≥ 100 and < 126 mg/dL on two consecutive occasions OR HbA1c ≥ 5.7 and $< 6.5\%$
Diabetes to Diabetes (no change)	Fasting glucose ≥ 126 mg/dL on Screening and Day 1 OR HbA1c $\geq 6.5\%$	Fasting glucose ≥ 126 mg/dL on two consecutive occasions OR HbA1c $\geq 6.5\%$

*No change (Normal to Normal, Impaired to Impaired, and Diabetes to Diabetes), Worsened (Normal to Impaired, Normal to Diabetes, and Impaired to Diabetes), and Improved (Impaired to Normal, Diabetes to Impaired, and Diabetes to Normal) categories will also be summarized.

**If one fasting glucose value is missing (Screening or Day 1), the assessment will be based on the available data.

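### In the glucose shift table (SAP 6.4.8.3.3), the discordant-pair rule can place two abnormal glucose values in Normal, and Impaired and Diabetes overlap with no precedence

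*SAP*

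**What the plan says.** SAP 6.4.8.3.3 classifies each subject at baseline and on treatment (once on the worst values, once on the last) and then groups the shifts as No change, Worsened or Improved. HbA1c figures are in per cent. The post-baseline rows are:

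- Normal: "Fasting glucose <100 mg/dL on two consecutive occasions AND HbA1c <5.7".
- Impaired: "Fasting glucose ≥100 and <126 mg/dL on two consecutive occasions OR HbA1c ≥5.7 and <6.5".
- Diabetes: "Fasting glucose ≥126 mg/dL on two consecutive occasions OR HbA1c ≥6.5".

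Text above the table covers incomplete or discordant data. The trigger is "If consecutive fasting glucose measurements fall in two separate categories, or if only one pre- or post-baseline fasting glucose measurement is available", and the consequence is "then the classification will be based on the HbA1c measurements only". A further rule covers absent HbA1c: "If HbA1c is missing then both consecutive fasting glucose measurements must fall in a category otherwise the lower category will be used". A footnote to the baseline column says "If one fasting glucose value is missing (Screening or Day 1), the assessment will be based on the available data".

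**The concern.** A category scale should not improve when glucose rises, and each subject should land in one cell. The text fails on both counts for some subjects.

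First, a discordant pair is discarded in favour of HbA1c even when both readings are abnormal. The subject can then be called Normal without meeting the table's own definition of Normal. Second, Impaired and Diabetes can each be met through a different marker, and nothing says which prevails. The cell then depends on how the program is written.

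The table is one of the four diabetes assessments listed in SAP 6.4.8.3, in a trial that enrols people with type 2 diabetes. At stake is whether its Worsened, No change and Improved counts are uniquely defined and point the right way.

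**Working it through.** **Inputs (all from SAP 6.4.8.3.3).** Glucose cut-points are 100 and 126 mg/dL and HbA1c cut-points are 5.7% and 6.5%, with the rows and rules set out above. The SAP states no figure for this rule, so there is none to reproduce. The check is to apply the text case by case.

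| Glucose pair (mg/dL) | HbA1c | Rule that applies | Result |
|---|---|---|---|
| 101, 101 | 5.6% | Impaired row | Impaired |
| 120, 120 | 5.6% | Impaired row | Impaired |
| 130, 120 | 5.6% | discordant, HbA1c only | Normal |
| 200, 125 | 5.6% | discordant, HbA1c only | Normal |
| 130, 130 | 5.6% | Diabetes row | Diabetes |
| 130, 120 | missing | lower glucose category | Impaired |
| 110, 110 | 6.6% | Impaired row and Diabetes row | both |
| 130, 130 | 6.0% | Impaired row and Diabetes row | both |

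Rows 2 and 3 show the reversal: the higher pair gets the better category. Rows 3 and 6 show that adding a normal HbA1c turns Impaired into Normal.

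**All combinations.** First glucose category × second glucose category × HbA1c category = 3 × 3 × 3 = 27.

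- Discordant pairs: 6 × 3 = 18.
  - In 12 of these HbA1c is Impaired or Diabetes. HbA1c then meets its own row, and it is at least as high as the lower glucose category, which can be at most Impaired. These are unproblematic.
  - In the other 6 HbA1c is below 5.7%. No table row is met, and the tie-break gives Normal. In 4 of them one glucose value is below 100, so Normal is defensible. In the remaining 2 (one Impaired and one Diabetes value, in either order) both values are at least 100.
- Concordant pairs: 3 × 3 = 9. Seven meet exactly one row. Two meet both Impaired and Diabetes.

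Problem combinations: 2 + 2 = 4 of 27.

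**Effect on shifts.**

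- 95, 95, 5.5% to 130, 120, 5.6%: Normal to Normal, so No change.
- 110, 110, 5.6% to 130, 120, 5.6%: Impaired to Normal, so Improved.
- Baseline Impaired on HbA1c 6.0%, then 130, 130, 6.0%: fits both No change and Worsened.
- 130, 120, 5.6% to 120, 120, 5.6%: Normal to Impaired, so Worsened, if the tie-break is also applied at baseline.

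**How often the tie-break is triggered.** The documents give no within-subject variability. Assume normal readings X with a coefficient of variation (CV) of 5–8% and a usual value of 120–130 mg/dL. The chance that two readings straddle 126 is 2 × P(100 ≤ X < 126) × P(X ≥ 126).

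- Usual value 120, CV 5% (SD 6): 2 × 0.841 × 0.159 = 0.27.
- Usual value 126, CV 5%: 2 × 0.5 × 0.5 = 0.50.

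The range is 27–50%. It describes the trigger only: a move to Normal also needs HbA1c below 5.7% in the same subject.

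**Single glucose value at baseline.** Suppose Screening is missing, Day 1 is 120 mg/dL and HbA1c is 5.6%. The text gives Normal, from HbA1c alone. If the footnote's available data means the remaining glucose value, the result is Impaired. If it means HbA1c, the two agree. The wording does not settle which is meant.

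**The case against.** Treating two disagreeing glucose readings as unconfirmed and deferring to HbA1c is a recognisable choice. It fails only where both readings are at least 100 and HbA1c is below 5.7%. That stands, and it limits the first defect to 2 of 27 combinations. On overlap, the worst-on-treatment table hints at taking the worse category. The SAP does not say so, and the hint does not help the last-on-treatment table or the baseline category.

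Other analyses also catch much of what this table might lose:

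- SAP 6.4.8.2 plans worst-value shift tables, including one for fasting glucose and one for HbA1c in three exclusive bands.
- SAP 6.4.8.3.2 summarises worst and last on-treatment glucose and HbA1c separately.
- SAP 6.4.8.3.4 counts two consecutive glucose values of at least 126, any HbA1c of at least 6.5%, new anti-diabetic medication and diabetic adverse events in subjects without diabetes at baseline.

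This also stands. None of these repairs the combined glucose-and-HbA1c category in 6.4.8.3.3.

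A reader might infer more than the documents support:

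- **That the table's counts are invalid throughout.** 23 of the 27 combinations are classified uniquely and without this inversion.
- **That hyperglycaemia near 126 mg/dL is generally moved to Normal.** With HbA1c of 5.7 to below 6.5% the same pair is Impaired, and with 6.5% or more it is Diabetes.
- **That 27–50% of subjects near the threshold are misclassified.** That figure is a trigger probability under an assumed CV.
- **That the rule favours inclisiran.** It is identical in both arms, and errors can run either way, as the last shift example shows.
- **That the text and footnote flatly contradict each other.** The footnote does not say which data. Similar wording in 6.4.8.3.2, attached to averaged glucose values, makes the glucose reading plausible but not certain.

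**Conclusion.** The point holds in a limited form. As written, the rule gives a wrong-direction category in 2 of 27 combinations and a non-unique one in another 2, so some shifts are reported as Improved or No change when glucose has risen, or fit two cells. The single-glucose text and the footnote are ambiguous together.

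This rests on a literal reading of 6.4.8.3.3. The 27 are combinations of categories, not subjects. The number of subjects affected cannot be derived, because the documents give neither the frequency of discordant pairs nor the joint distribution of glucose and HbA1c. The table is descriptive and carries no hypothesis test, and the efficacy conclusions do not depend on it. It is worth correcting because the stated rule cannot be programmed to a unique answer.

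**What to change.** Replace the classification rule in SAP 6.4.8.3.3 with the following, applied identically at baseline and post-baseline:

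1. Glucose category: the lower of the two consecutive categories. This extends the SAP's own rule for missing HbA1c, "otherwise the lower category will be used".
2. HbA1c category: from its own cut-points.
3. Final category: the higher of 1 and 2. If HbA1c is missing, use 1 alone.

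With categories scored 0, 1, 2, final = max(min(g1, g2), h), where g1 and g2 are the glucose categories and h is the HbA1c category. Each of the 27 combinations then has one category, and raising a glucose value can never lower it. The pair 130, 120 with 5.6% becomes Impaired. The pairs 110, 110 with 6.6% and 130, 130 with 6.0% become Diabetes only. The other 23 combinations are unchanged.

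State one rule for a single glucose value and align the footnote with it. A single post-baseline value should not establish Diabetes. Otherwise one reading of 130 with HbA1c 5.5% would be Diabetes while 130 followed by 120 would be Impaired, so a missing reading would worsen the category and the two-occasion requirement would be lost. Keeping HbA1c alone for a single post-baseline value avoids this. The text should also name which HbA1c is matched to each glucose pair, since SAP 3.8.8.3 omits HbA1c at Days 150, 330 and 510.

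Cost: SAP wording and one derivation in the safety programs. No change to the protocol or to data collection.
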